10.1 Specification, Timing and Recording of Safety Parameters

The following safety parameters will be recorded in the eCRF at the scheduled visits as per **Table 2**:

- Adverse events (as detailed in 10.2)
- Episodes of infection not requiring hospital admission
- Antibiotic usage (number of episodes)
- Nausea for >72 hours following IMP administration.
- Abdominal pain or discomfort for >72 hours following IMP administration.
- Diarrhoea >7 days following IMP administration.

*Diarrhoea is defined in this study according to the World Health Organisation as the passage of three or more loose or liquid stools per day (or more frequent passage than is normal for the individual). Frequent passing of formed stools is not diarrhoea. If participants are taking lactulose or other aperients, these must have been stopped for 72-hours before diarrhoea can be diagnosed.

The following liver-related events, if leading to hospitalisation, will require expedited reporting to KHP-CTO:

- Liver disease progression
- Any known complication of cirrhosis including variceal bleeding, new-onset ascites, hepatic encephalopathy, spontaneous bacterial peritonitis, hepatorenal syndrome, acute-on-chronic liver failure and sepsis.
- Recurrence of ascites or jaundice
- Hepatocellular carcinoma
- Death as a result of a known complication of cirrhosis or disease progression.

10.2 Procedures for Recording and Reporting Adverse Events

Any Adverse Event (AE) or Serious Adverse Event (SAE) will be reported from the time of consent.

The Medicines for Human Use (Clinical Trials) Regulations 2004 and Amended Regulations 2006 gives the following definitions:

- 1. Adverse Event (AE): Any untoward medical occurrence in a participant to whom a medicinal product has been administered, including occurrences which are not necessarily caused by or related to that product.
- **2.** Adverse Reaction (AR): Any untoward and unintended response in a participant to an investigational medicinal product which is related to any dose administered to that participant.

- 3. Unexpected Adverse Reaction (UAR): An adverse reaction the nature and severity of which is not consistent with the information about the medicinal product in question set out in the Investigator's Brochure (IB).
- 4. Serious Adverse Event (SAE), Serious Adverse Reaction (SAR) or Suspected Unexpected Serious Adverse Reaction (SUSAR): Any adverse event, adverse reaction or unexpected adverse reaction, respectively, that:
 - o results in death;
 - is life-threatening;
 - o required hospitalisation or prolongation of existing hospitalisation;
 - o results in persistent or significant disability or incapacity;
 - consists of a congenital anomaly or birth defect.
- 5. Important Medical Events (IME) & Pregnancy: Consideration for Liver Transplantation will be deemed as an IME and will require expedited reporting to KHP-CTO. Events that may not be immediately life-threatening or result in death or hospitalisation but may jeopardise the participant or may require intervention to prevent one of the other outcomes listed in the definition above should also be considered serious. Although not a serious adverse event, any unplanned pregnancy will also be reported *via* the SAE reporting system.

Reporting Responsibilities

King's College Hospital NHS Foundation Trust and King's College London have delegated the delivery of the Sponsor's responsibility for Pharmacovigilance (as defined in Regulation 5 of the Medicines for Human Use (Clinical Trials) Regulations 2004 to the King's Health Partners Clinical Trials Office (KHP-CTO).

All SAEs, SARs and SUSARs (excepting those specified in this protocol as not requiring reporting) will be reported immediately (and certainly no later than 24 hours) by the Investigator to the KHP-CTO and Chief Investigator for review in accordance with the current Pharmacovigilance Policy. The KHP-CTO will make the expectedness assessment against the Reference Safety Information section of each Investigational Medicinal Product. If the sponsor or the CI does not agree with the investigator's causality assessment the opinion of both the investigator and the Sponsor will be provided with the report. The adverse event log (AEL) will be reviewed at each trial assessment clinic visit and at follow-ups and following any occurrences in between study visits and follow-ups.

Death as a result of disease progression and other events that are primary or secondary outcome measures are not considered to be SAEs and should be reported in the normal way, on the appropriate CRF.

On a scheduled basis, the Data Monitoring Committee (DMC) will review adverse event information. The KHP-CTO will report SUSARs to the regulatory authorities (MHRA, competent authorities of other EEA (European Economic Area) states in which the trial is taking place.

The Chief Investigator will report to the relevant ethics committee. Reporting timelines are as follows:

- SUSARs, which are fatal or life-threatening must be reported not later than 7 days after the sponsor is first aware of the reaction. Any additional relevant information must be reported within a further 8 days.
- SUSARs that are not fatal or life-threatening must be reported within 15 days of the sponsor first becoming aware of the reaction. The Chief Investigator and KHP-CTO (on behalf of the co-sponsors) will submit a Development Safety Update Report (DSUR) relating to this trial IMP, to the MHRA and REC annually.

10.3 Premature Termination of the Trial

The PROMISE trial may be prematurely discontinued by the Sponsor, Chief Investigator or Regulatory Authority on the basis of new safety information or for other reasons given by the Data Monitoring and Ethics Committee, Trial Steering Committee, Regulatory Authority or Ethics Committee concerned.

If the trial is prematurely discontinued, active participants will be informed, and no further participant data will be collected. The Competent Authority and Research Ethics Committee will be informed within 15 days of the early termination of the trial.

11 Statistics

A Statistical Analysis Plan (SAP) will be drafted during the trial and will be finalised prior to the trial statistician becoming partially blinded (able to view participants and outcome partitioned and coded as A/B). The SAP will cover all of the trial analysis details.

11.1 Sample Size

Moreau *et al.* ⁴¹ performed a double-blind trial of the long-term fluoroquinolone antibiotic norfloxacin *versus* placebo in 291 patients with advanced cirrhosis (Child Pugh C) who had not received recent fluoroquinolone therapy. The study was performed at 18 clinical sites in France. Patients were randomly assigned to groups given 400mg norfloxacin (n=144) or placebo (n=147) once daily for 6 months. The primary outcome was 6-month mortality, as estimated by the Kaplan-Meier method. The Kaplan-Meier estimate for 6-month mortality was 14.8% for patients receiving norfloxacin and 19.7% for patients receiving placebo (p=0.21). In competing risk analysis that took liver transplantation into account, the cumulative incidence of death at 6-months was significantly lower in the norfloxacin group than in the placebo group (sub-distribution hazard ratio, 0.59; 95% confidence interval, 0.35-0.99). Norfloxacin significantly decreased the incidence of any and Gram-negative bacterial infections without increasing infections caused by *Clostridioides difficile* or multidrug-resistant bacteria. We have estimated FMT to be at least as effective as norfloxacin to reduce infection (hazard ratio = 0.625). ⁴⁴

We have assumed that 65% of patients in the control group experience an infection resulting in hospitalisation within 2-years and that this is reduced to 48.9% in the FMT arm. In order to detect this hazard ratio of 0.625, with 80% power (alpha = 0.047) we would need to analyse 270 patients (to experience 155 events). In order to account for a 10% loss to follow up, we will inflate to 300 patients (1:1 ratio). Note: 203 events would provide 90% power to detect this

effect, and 261 events would provide 80% power to detect a HR = 0.70. Using a group sequential design, an interim analysis will be carried out after 81 events (alpha = 0.006).

11.2 Recruitment

Trial recruitment will be monitored closely by the Trial Manager and reported at the TMG meetings. Anonymised participant pre-screening logs will be requested by sites and assessed on an ongoing basis. Section 4.4 outlines how participants will be identified for inclusion in the trial.

Additionally, the KCTU Standard Operating Procedures (SOPs) will guide the trial statistician's reports outlining recruitment numbers across the trial and at site level to the DMC. The DMC will be consulted to advise on potential strategies where there are recruitment difficulties *i.e.,* including but not limited to; modifications to the inclusion/exclusion criteria, targeted recruitment drives, escalation at site level to PI/R&D, opening additional study centres or site closure.

11.3 Analysis

Primary Outcome: The number of days from randomisation to first infection ³² leading to hospital admission.

Assessment of efficacy:

The main analysis will include all randomized participants (eligibility as defined in section 7) in the arms to which they were randomized, regardless of what treatment they received postrandomisation, with the intent to estimate an intention-to-treat (ITT) type estimand. For the primary analysis, a treatment policy strategy will be used for any intercurrent events (such as discontinuation of treatment or death), that is the occurrence of the intercurrent event will be considered irrelevant in defining the treatment effect of interest. Sensitivity analyses will examine this assumption using different strategies for the intercurrent events. Population definitions, target estimands and handling of intercurrent events will be further described in the Statistical Analysis Plan.

Primary analysis: A Cox baseline proportional hazards model of the time to infection will be fitted with frailty effect to account for site heterogeneity, adjusted for baseline disease severity, participant age, sex and baseline cirrhosis severity. The adjusted hazard ratio will be presented with associated 95% confidence interval. Proportionality will be assessed using a Kaplan Meier survival and log-log plots.

Secondary analysis:

Time to event outcomes including mortality (all-cause; liver-related), hospitalisation, progression to ACLF ³³ and hepatic decompensation will be analysed in a manner consistent with the primary analysis.

Binary outcomes (infection rates, AMR incidence and antibiotic usage) will be analysed with a mixed-effects multivariable logistic regression, fitting a random effect for site, and fixed effects for: participant age, sex, baseline disease severity.

Continuous outcomes (liver disease severity scores; AUDIT score; HADS score; EQ-5D-5L score) will be analysed using a mixed effects multivariable regression, adjusted in a consistent manner with the primary outcome analysis including baseline version of the outcome if applicable.

Missing data and population under investigation:

Missing data will be quantified and explored for structure and breaches to the assumption of missing at random. If missing outcome data is greater than 5%, predictors of missing outcomes will be explored and if post-randomisation variables predict missingness, multiple imputation considered.⁴⁵ The primary population will include all randomised participants regardless of subsequent events (an "intention to treat" population). A sensitivity analysis of the primary outcome will be carried out to estimate the treatment effect for those participants who complied with the intervention (a "per-protocol" type population), by estimating the complier average causal effect.⁴⁶

Subgroup analyses:

The following subgroups will be used to explore for moderating effect: sex; participant age; baseline disease severity, socioeconomic status (using the index of multiple deprivation), and additional factors if determined as important by the Trial Steering Committee. ⁴⁵

Adherence: Participant adherence will be determined by participants taking >70% of their allocated intervention.

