5.3 Secondary endpoints

- 1. Incidence of decompensating events including hepatic encephalopathy, new-onset ascites, variceal bleeding and spontaneous bacterial peritonitis over 24 month follow up period.
- 2. Progression to ACLF (the development of one or more organ failures). ³³
- 3. Infection rates and antibiotic usage following randomisation over 24 month follow up period.
- Incidence of AMR including skin and nose colonisation with methicillin-resistant Staphylococcus aureus (MRSA), vancomycin-resistant Enterococci (VRE), linezolidresistant Enterococci (LRE), extended-spectrum beta-lactamase producing bacteria (ESBL), fluoroquinolone-resistant Gram negative and carbapenem-resistant Enterobacterales (over 24 month follow up period).⁸
- 5. Hospitalisation rates (liver-related and all-cause) including the length of stay and admission to high dependency/intensive care (over 24 month follow up period).
- 6. Change in liver disease severity scores over 24 months post-randomisation (recorded every 3 months).
- 7. Change in quality of life (EQ-5D-5L score) at 3, 6, 12 and 24 months post-randomisation.
- 8. All-cause mortality, and liver-related mortality.
- 9. Change in depression and anxiety score using HADS at 3, 6, 12 and 24 months postrandomisation
- Change in alcohol use disorder-related events in patients enrolled with alcohol-related cirrhosis as assessed by the alcohol-use disorders identification test (AUDIT score) ³³ at 3, 6, 12 and 24 months post-randomisation, and urinary ethyl glucuronide/ethyl sulphate levels if tested as part of the standard of care.
- 11. Safety based on safety assessments including physical examination, clinical laboratory evaluation, vital signs and reported as adverse events (AEs) or serious adverse events (SAEs) over 24 month follow-up period.

Mechanistic endpoints:

- 1. **Matched faecal and plasma biomarkers** (D-lactate, fatty acid- binding protein 2 and ammonia) measured by enzyme-linked immunosorbent assay (ELISA).
- 2. **Faecal proteases** as markers of DNA replication, tissue re-modelling and immune response as a proxy of gut mucosal barrier integrity.
- Matched plasma and faecal cytokine profiles using a combination of ELISA and by electrochemiluminescence using the Mesoscale discovery platform (MSD) [Tumour necrosis factor-alpha, interferon-gamma, interleukin (IL)-1-beta, IL-6, IL-8, IL-10, IL-17A, IL-17E, IL-17F, IL-21 and IL-22].

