7.8 Expected Duration of Trial

Recruitment will be carried out for approximately 18-months and follow-up will be carried out for at least 2-years, and in the last 6-months, we plan to analyse, report, and disseminate. At the end of one year after the first site being opened to recruitment, we will assess recruitment rates and the feasibility of continuing the PROMISE trial. Each individual participant will remain on trial for 24 months from the date of treatment.

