9.1.2 Secondary Efficacy Parameters

- To evaluate the efficacy of encapsulated FMT to reduce **decompensating cirrhotic events**: (i) acute variceal bleeding, (ii) new onset ascites, (iii) spontaneous bacterial peritonitis, (iv) hepatic encephalopathy and (v) development of acute-on-chronic liver failure (the development of one or more organ failures). ³³
- To evaluate the impact of encapsulated FMT on all-cause hospitalisation documenting
 (i) length of stay and (ii) requirement for high dependency and intensive care.
- To assess the impact of encapsulated FMT on (i) antibiotic usage episodes and (ii) development of antimicrobial resistance as measured by colonisation with methicillinresistant Staphylococcus aureus (MRSA), vancomycin-resistant *Enterococci* (VRE), extended spectrum beta-lactamase producing bacteria (ESBL), linezolid-resistant *Enterococci* (LRE) and fluoroquinolone-resistant Gram negative and carbapenemresistant Enterobacterales (CRE). ⁸
- Change in liver disease severity scores (Child Pugh, ³⁹ MELD ²⁸ and UKELD ⁴⁰).
- All-cause and liver-related mortality.
- Change in **quality of life** (EQ-5D-5L questionnaire).
- Change in HADS score.
- Change in the alcohol-use disorders identification test (AUDIT score) ³³ and urinary ethyl glucuronide/ethyl sulphate levels recorded if tested as part of the standard of care in participants with alcohol-related or MASLD-ALD Overlap cirrhosis.

10 Assessment of Safety

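### Infection rates and antibiotic usage are recorded as episodes but analysed as yes/no without follow-up time, which discards repeat episodes and biases the comparison against FMT if FMT lowers mortality

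*Protocol*

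**What the plan says.** The secondary endpoint in section 5.3 is "Infection rates and antibiotic usage following randomisation over 24 month follow up period". Section 9.1.2 names the antibiotic parameter as "antibiotic usage episodes". Section 10.1 lists "Antibiotic usage (number of episodes" and "Episodes of infection not requiring hospital admission" among the data recorded in the eCRF. Section 6.2 stops study medication at the first hospitalised infection but keeps the participant in follow-up, so later episodes can be observed.

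Section 11.3 then classifies the outcomes: "Binary outcomes (infection rates, AMR incidence and antibiotic usage) will be analysed with a mixed-effects multivariable logistic regression". Besides treatment, the only terms named for that model are site (random), age, sex and baseline severity. It lists no follow-up term or offset. The treatment-policy handling of death is stated for the primary analysis; no rule for death is stated for these secondary outcomes.

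Planned follow-up is the same for everyone. Section 7.8 says: "Each individual participant will remain on trial for 24 months from the date of treatment".

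**The concern.** A rate or a number of episodes is not a binary outcome. Fitting a logistic model means reducing each participant to any episode or none, with two consequences.

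- **Repeat episodes are discarded.** Section 11.1 expects 65% of controls to have at least one infection leading to admission. Adding non-admitted infections can only raise the share with any infection, so more of the remaining information lies in the repeats.
- **Time at risk is ignored.** A participant who dies uninfected at month 3 is either coded as infection-free, exactly like someone observed for 24 months, or has no defined outcome. Section 5.1 gives reducing infection and mortality as the trial's aim. If FMT does lower mortality, its participants are exposed to infection for longer, and a yes/no comparison turns that into apparent harm.

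Secondary objective 3 (antibiotic use) and the infection-rate endpoint support the case for FMT as an alternative to antibiotics, so a diluted or biased result here would matter to how the trial is read.

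**Working it through.** **The plan's own figures.** No power is stated for these secondary outcomes. The primary figures reproduce: Freedman's formula at hazard ratio 0.625, alpha 0.047 and 80% power gives 151 events (155 stated); 155 / [(0.65 + 0.489)/2] = 272 patients (270 stated); 270/0.9 = 300.

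**Inputs.** From section 11.1: 65% of controls with an event at 2 years, 135 analysed per arm, and ratio 0.625, applied here as a rate ratio. Assumed, because the protocol gives none: overdispersion k, episode rates above the implied one, and 24-month mortality. With k = 0, 65% implies a control mean of m = -ln(0.35) = 1.05 episodes per 2 years, or 0.525 per year.

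**1. Information lost if the effect persists throughout** (two-sided 0.05)

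Yes/no: p = 1 - exp(-m) for k = 0, otherwise 1 - (1 + km)^(-1/k), with the usual two-proportion power. Count: Var(log RR) = [1/m + 1/(0.625m) + 2k]/135.

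For k = 0: p0 = 0.650 and p1 = 1 - exp(-0.656) = 0.481 (the plan states 48.9%; the gap is immaterial here), giving 80% power. Count: Var = (0.953 + 1.524)/135 = 0.01834, SE 0.1354, z = 0.470/0.1354 = 3.47, power 93%.

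| k | m | yes/no | count |
|---|---|---|---|
| 0 | 1.05 | 80% | 93% |
| 0.5 | 1.05 | 62% | 83% |
| 1 | 1.05 | 48% | 73% |
| 0.5 | 1.38 (keeps 65%) | 63% | 90% |
| 1 | 1.86 (keeps 65%) | 47% | 84% |

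At m = 1.05 the loss is 13 to 25 points. With m raised so that 65% still holds under overdispersion, it is 27 points at k = 0.5 and 37 at k = 1.

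**2. The same comparison with the medication stop included**

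Simulation: 135 per arm, true rate ratio 0.70, 15% deaths, k from 0.5 to 1.0, hospitalised infections at 0.525 per year, and the FMT effect assumed to end 3 months after that admission.

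| episodes per year | yes/no | count |
|---|---|---|
| 0.8 | 29-39% | 26-36% |
| 1.2 | 24-34% | 30-46% |
| 2.0 | 22-31% | 39-57% |

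The estimated rate ratio moves from 0.70 to about 0.8. A repeat of this simulation gave 27-53% for the count model against 24-34% for yes/no; without the stop, the count model had 58-89%. Allowing for simulation error, the gain with the stop is about 0 to 27 points.

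**3. Survival bias with no true effect on infection**

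Let infection hazard be λ = 0.525 per year in both arms and death hazard h = -ln(1 - mortality)/2. Then P(infection observed) = λ/(λ + h) × [1 - exp(-2(λ + h))].

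- Control mortality 25%: h = 0.144, P = 0.579.
- FMT mortality 16%: h = 0.087, P = 0.605. OR = (0.605/0.395)/(0.579/0.421) = 1.12.
- FMT mortality 10%: h = 0.053, P = 0.623. OR = (0.623/0.377)/(0.579/0.421) = 1.20.
- Equal mortality: identical P, so OR = 1.00.

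Simulation agrees: OR 1.12 with 8% false positives, and 1.20 with 10.5%, while the rate ratio using follow-up time stays at 1.00-1.01. With 30% control mortality and mortality hazard ratio 0.59 (the sub-distribution figure quoted in section 11.1 from the norfloxacin trial, borrowed as an assumption), m = 1.05 and k from 0 to 1, the OR is 1.10-1.14 and false positives are 8-9%. With 15% versus 10% deaths the OR is only 1.04-1.08.

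**4. Effect on power with a true rate ratio of 0.625** (m = 1.05, k = 0, 150 per arm, 10% loss, 30% control mortality): logistic power is 73% with equal mortality and 57% with mortality hazard ratio 0.59. The rate model keeps 91-92%.

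These calculations are unadjusted and omit site effects.

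**The case against.** The strongest objection concerns power. Study medication stops at the first hospitalised infection, and section 4 reports that the benefit waned by day 90 in the feasibility study. Later episodes are therefore largely off treatment, and a yes/no outcome is weighted towards the on-treatment period. This stands in part: it removes the count model's advantage at the lowest rate examined, reduces it elsewhere, and dilutes the rate ratio. It does not make the count model materially worse in any setting examined.

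A reader might infer that the yes/no analysis loses most of the power. The documents do not support that: at the plan's implied rate the loss is 13-25 points, and larger losses need episode rates and dispersion that the protocol does not give. Nor is follow-up unequal by design. It is 24 months for all, section 7.7 seeks routine outcome data after withdrawal, and section 11.3 considers multiple imputation for missing outcomes. Inequality arises only through death, loss or withdrawal, and the survival bias needs mortality to differ between arms.

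Two wider inferences also fail. Hospitalisation is already assigned to time-to-event analysis in section 11.3. A yes/no analysis of antimicrobial resistance is not contradictory in itself, and the scheduled stool samples could not replace the skin and nose colonisation named in section 5.3.

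Finally, the SAP may add detail on estimands and intercurrent events. Outcome type and model, however, are already fixed in the protocol, and they conflict with its own endpoint definition.

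**Conclusion.** The mismatch is real and lies in the stated text: outcomes defined or recorded as rates and episodes are declared binary and modelled without follow-up time. Repeat episodes are discarded, and early uninfected deaths count as infection-free or are left undefined.

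The bias is conditional. Under assumed control mortality of 25-30% and lower FMT mortality, the null odds ratio is about 1.1-1.2 against FMT with roughly 8-10% false positives; with equal mortality it is nil. The protocol gives no 24-month mortality for this population, so these are illustrations over a range.

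The power gain from counts is substantial if the effect persists and small to moderate, about 0-27 points, if it ends soon after medication stops. The case for change rests on the match to the endpoint and on protection from survival bias, with power as a secondary gain of uncertain size. The point is limited to infections and antibiotic usage.

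**What to change.** In section 11.3, and in the SAP to match, move infections and antibiotic usage out of the binary list. Analyse the number of infections and the number of antibiotic courses by mixed-effects negative binomial regression with log(follow-up time) as offset, a random effect for site and the same fixed effects. Report rate ratios, and state that death ends time at risk. Keep the any-event logistic analysis as supportive, with an explicit rule for participants who die or are lost before 24 months.

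The cost is small. Episodes are already recorded under section 10.1, so this is a wording change. A dispersion parameter must be estimated. The rate ratio will include off-treatment episodes after the first hospitalised infection, so it is diluted relative to the on-treatment effect, and the text should say so.
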